#### Time to First Overall Response

The treatment policy strategy will be applied. The time to overall response (based on the above definition) prior to HSCT will be estimated as described below regardless of any potential intercurrent events.

Time to first Overall Response is defined as time from the date of first dose of emapalumab to the first achievement of response ([refer to Section 6.2.2](#)). Patients with no response will be censored at the date of EOT visit or last assessment. Time to first response prior to HSCT will be presented by Kaplan-Meier curve with median calculated if available. Associated two-sided 95% confidence intervals will be calculated for the median.

#### Cumulative Duration of Response

The treatment policy strategy will be applied. The cumulative duration of response will be estimated as described below regardless of any potential intercurrent events.

Cumulative duration of response is defined as total time in response from the first achievement of an Overall Response until EOT ([refer to Section 6.2.2](#)). For patients who achieve a response, lost that response, and then achieve it subsequently, the total time in response will be calculated by adding together these separate periods in response. The cumulative duration of response will be calculated under the hypothetical assumption that a patient's response achieved at any visit will maintain up until the next visit. Patients who do not achieve response at least once between the date of first dose and EOT will be excluded from the analysis. Cumulative duration of response will be summarized using descriptive statistics.

#### Ability to Reduce Glucocorticoids

The ability to reduce glucocorticoids by 50% will be defined as reduction in the equivalent dose from baseline by at least 50% and maintained for at least 7 days.

Baseline will be defined as the equivalent dose on the day before first infusion (SD-1). If the equivalent dose on the day before first infusion (SD-1) is not available, then the equivalent dose before first infusion that is closest to SD0 will be used.

The equivalent dose will be calculated as follows:

The equivalent dose will include only glucocorticoids administered orally (PO) or intravenously (IV) (route of "Oral", "Intravenous injection", or "Intravenous injection drip" as collected in the CRF). IV and PO routes of administration are considered dose-equivalent in the analysis.

- $\text{Daily dose} = \text{Conversion factor} \times \text{Dose of glucocorticoids in mg} \times \text{number of administrations per day}^*$   
\* If two or more different glucocorticoids were administered in one day then the total daily dose would equal the sum of daily doses for each glucocorticoid.
- $\text{BSA Surface Area (BSA)} = \text{Height (cm)} \times \text{Weight (kg)} / 3600$
- $\text{Equivalent dose (mg/m}^2\text{/day)} = \text{Daily dose} / \text{BSA}$

The conversion factors for glucocorticoids are listed as below:

Glucocorticoids	Conversion factor
Dexamethasone	1
Methylprednisolone	1/5.3
Prednisolone	1/6.7
Prednisone	1/6.7
Triamcinolone	1/5.3
Hydrocortisone	1/26.6
Cortisone	1/33.3

The number of administrations per day will be assigned based on dose frequency collected in the CRF:

Dose frequency	Number of administrations per day
Once a day	1
Twice a day	2
Thrice a day	3
Once every two days	0.5
Single administration	1
As needed	1
Unknown	1
Other	1

The treatment policy strategy will be applied. The ability to reduce glucocorticoids will be estimated as described below regardless of any potential intercurrent events.

The number and percentage of subjects able to reduce glucocorticoids by 50% or more of the baseline dose during emapalumab treatment will be provided.

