6.4.5 Prior and concomitant therapy

A prior and concomitant therapy is any drug or substance administered from the screening visit until the EOS visit. The investigator must instruct patients and/or legal representatives to notify the study site about any new medications taken after the patient has been screened for the study. All medications, non-drug therapies (including physical therapy and blood transfusions) administered after the patient was enrolled must be recorded in the eCRF. Information about medication name, indication, dose, unit, frequency, route date and time is to be recorded for each medication.

Any conventional treatment for pHLH (including but not limited to plasmapheresis, HSCT) must be recorded, regardless of when it has been received.

No other medicinal product under investigation may be used concomitantly with the IMP in this study.

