Baseline will be defined as the last available measurement or recording prior to the first study drug administration. For assessments performed only on screening visit prior to the first emapalumab infusion, the measurement or the recording of the screening visit will be used as baseline. For

assessments that are also performed pre-infusion on visit 1 in addition to screening visit, the measurement or recording pre-infusion on visit 1 will be used. If the measurement or recording pre-infusion on visit 1 is not available, then the measurement or recording of the screening visit will be used.

Unless otherwise noted, descriptive statistical summary will only include data from scheduled visits or time points. Data from unscheduled visits or time points will be presented in data listings. For data of quantitative measurements but are collected with characters such as “>/≥” or “</≤”, the numeric part of the value will be used in the descriptive analysis. For other cases where characters are entered for quantitative measurements, the result will not be used in the descriptive analysis but only included in data listing.

If deemed necessary, specific data points may be excluded from the analysis based on related discussion in the data review meeting (DRM). The decisions and reason(s) for exclusion will be documented separately in Resolution of Data Review Meeting in detail.

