## **6.5. Exposure and Compliance**

IMP administration including level of dose prescribed, prescribed dose, date, time and duration of dose administration, and information on dose increase and dose interruption will be collected in the CRF.

The total prescribed dose, total dose administered, total duration of dosing (in days), and average dose frequency (times per day) will be summarized using descriptive statistics. The dose administered will be calculated based on prescribed dose and approximate proportion administered (refer to [Section 6.2.2](#)). The total duration of dosing will be calculated based on the date of last infusion and the date of first infusion (refer to [Section 6.2.2](#)). The average dosing frequency will be calculated based on the total duration of dosing and the total number of records of emapalumab infusion (refer to [Section 6.2.2](#)).

The emapalumab dose change from the first dosing will be summarized showing the number and percentage of patients with a dose increase or a dose decrease at each visit. Moreover, the percentage of dose increases and decreases from the first dose for each patient will be summarized using a descriptive table. Percentage of dose increase or decrease from first dose will be calculated based on prescribed dose at first dosing and prescribed dose at each visit (refer to [Section 6.2.2](#)).

Data listing containing all information collected for IMP administration will be provided. In addition, IMP administration will be listed at patient level including all dose adjustments over time and summarized in terms of the number of doses administered, maximum dose, equivalent dose of dexamethasone, duration of exposure from the first dose to the last dose of treatment, cumulative dose, average dose frequency and average dose per day.

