#### Weight and Height

Measured date and time, and subjects' weight will be collected at all scheduled visits during treatment period, and EOS visit of the follow-up period. Subjects' height will be collected at screening, week 8, EOT visit of the treatment period, and EOS visit of the follow-up period (for subjects older than 18 years old, height will only be collect at screening visit).

Weight and height will be summarized for screening visit and each applicable scheduled visit using descriptive statistics. Actual values and actual changes from baseline will be presented.

Listings will be provided for all height and weight measurements from scheduled and unscheduled visits.

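### The SAP's BSA formula prints without a square root, and its frequency table counts unclassified glucocorticoid schedules as once daily; both need correcting, but only the second can by itself misclassify the 50% reduction endpoint

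*SAP*

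**What the plan says.** SAP 6.8.2, Ability to Reduce Glucocorticoids, counts a patient as a success on a "reduction in the equivalent dose from baseline by at least 50% and maintained for at least 7 days". The dose compared is a dexamethasone-equivalent daily dose divided by BSA and labelled mg/m²/day. BSA is printed as "BSA Surface Area (BSA)} = \text{Height (cm)} \times \text{Weight (kg)} / 3600". The baseline dose is the equivalent dose on the day before the first infusion or, failing that, the closest earlier one.

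The daily dose is conversion factor × dose in mg × administrations per day. On the last term: "The number of administrations per day will be assigned based on dose frequency collected in the CRF". The lookup gives once daily 1, twice daily 2, thrice daily 3, every two days 0.5 and single administration 1. It also gives 1 to *As needed*, *Unknown* and *Other*. A footnote on totals reads: "If two or more different glucocorticoids were administered in one day then the total daily dose would equal the sum of daily doses".

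Three other places bear on this:
- SAP 6.1 gives a general baseline rule ("Baseline will be defined as the last available measurement or recording prior to the first study drug administration") but does not tie BSA to it.
- SAP 6.10.4 says that "weight will be collected at all scheduled visits during treatment period, and EOS visit of the follow-up period", so updated weights will exist.
- SAP 6.5 plans a per-patient exposure listing and summary that includes "maximum dose, equivalent dose of dexamethasone, duration of exposure from the first dose to the last dose of treatment". It gives no unit for the equivalent dose and no cross-reference to 6.8.2.

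**The concern.** There are two separate defects in how the dose is derived.

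The printed BSA does not behave like an area. If weight grows roughly as the cube of height, height × weight grows as the fourth power of length, while an area grows as the second power; the square root restores that. The trial enrols patients of any age, so a missing root would overstate doses in small children and understate them in large patients. The reported values would then not be in the unit on their label.

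The frequency table assigns one administration per day to records whose real schedule is something else or is not known. Four times daily and once weekly, for example, have no row. If such a schedule is coded *Other*, the daily dose is wrong. If the code also changes between baseline and follow-up, the endpoint can record a change in coding as a change in steroid dose, or miss a real one.

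Both bear on a named secondary efficacy endpoint whose method was the only listed change in SAP version 4.0.

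**Working it through.** The documents give no figure that depends on these rules, so there is nothing to reproduce. The body sizes, weight changes and schedules below are illustrative assumptions. The square-root form with the same divisor is also an assumption, since neither document states it. The 5 mg/m²/day is taken from protocol 6.4.5.1 only to set a scale.

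**1. BSA and the dose shown.** Let x = height × weight / 3600. Printed BSA = x and root BSA = √x, so the dose shown divided by the true dose is √x / x = 1/√x, which is 1/BSA. The two agree only where height × weight = 3600.

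| Height, weight | Printed BSA (x) | Root BSA (√x) | True 5 mg/m²/day is shown as |
|---|---|---|---|
| 75 cm, 9 kg | 0.188 | 0.433 | 11.5 |
| 100 cm, 16 kg | 0.444 | 0.667 | 7.5 |
| 140 cm, 35 kg | 1.361 | 1.167 | 4.3 |
| 170 cm, 65 kg | 3.069 | 1.752 | 2.9 |

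From the first row to the last, weight rises 65/9 = 7.2-fold and printed BSA rises 3.069/0.1875 = 16.4-fold. A surface area should not grow faster than weight, so the formula cannot be right as printed.

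**2. Effect on the 50% endpoint.** Reduction = 1 − (D₁/BSA₁)/(D₀/BSA₀). With one height and weight per patient, BSA₁ = BSA₀ and cancels: 4 mg to 2 mg gives 50% with or without the root.

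If BSA is instead updated with visit weight at constant height, let f be later weight divided by baseline weight. The cut in mg needed to score 50% is then 1 − 0.5f as printed, or 1 − 0.5√f with the root.

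| Weight change | As printed | With root | Fixed baseline size |
|---|---|---|---|
| −10% | 55.0% | 52.6% | 50% |
| +10% | 45.0% | 47.6% | 50% |
| +20% | 40.0% | 45.2% | 50% |

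**3. Frequency rule.** Take the case where the four-times-daily schedule is coded *Other*, so administrations per day = 1.
- 2 mg twice daily changed to 1 mg four times daily. True: 1 − (4 × 1)/(2 × 2) = 0%. Scored: 1 − (1 × 1)/(2 × 2) = 75% reduction, a false success if held for 7 days.
- 1 mg four times daily changed to 1 mg twice daily. True: 1 − (2 × 1)/(4 × 1) = 50% reduction. Scored: 1 − (2 × 1)/(1 × 1) = −100%, that is, a doubling and a false failure.

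If the same code and the same true frequency apply at both times, the error cancels.

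**4. Weight of one patient.** 100/10 = 10.0 percentage points at n = 10, and 100/18 = 5.6 at n = 18. This holds for any binary endpoint of this size. It shows what one error would cost, not how many errors to expect.

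**The case against.** The strongest reply is that the missing root may be a PDF-reading artefact, which would not be a defect of the plan. That stands: the documents as available do not prove that the issued page or the program lacks it. They do justify a check.

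A reader might infer that the missing root misclassifies patients on the 50% endpoint. The documents do not support that, because the factor cancels within a patient when one body size is used. A reader might also infer that the exposure listing in SAP 6.5 is wrong. That does not follow either: the section gives no unit and no link to 6.8.2, and its equivalent dose could be plain mg.

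On body size, current weight is a defensible choice in growing children, so a fixed baseline value is not the only correct one. With the root in place, a 10% weight change moves the required cut only to 47.6% or 52.6%, which matters only for patients near the threshold. What stands is that the SAP does not say which values to use.

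On frequency, setting catch-all codes to 1 is explicit and prespecified, and the 7-day rule means that one stray follow-up record would not by itself create a success. That limits the problem without removing it. A catch-all code that persists through follow-up satisfies the 7-day rule, and one at baseline enters every later comparison. A prespecified rule can still return a wrong daily dose.

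The footnote on totals mentions only different glucocorticoids, but it does not forbid summing several same-day records of one drug. This is missing detail, not an error.

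**Conclusion.** The point holds in a limited form and should be fixed.

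- **Formula.** As printed, it does not give m². If the issued page and program match the print, each mg/m²/day value is off by 1/BSA: about 2.3-fold too high at 75 cm/9 kg (11.5/5) and about 0.57 of the true value at 170 cm/65 kg (2.85/5). This rests on the root really being absent and on the square-root form being intended.
- **Frequency table.** This defect depends neither on the formula nor on PDF reading. It can misclassify a patient in either direction when unlisted schedules are coded *Other* and the coding changes between baseline and follow-up. CRF coding practice and the number of such records are not in the documents, so no misclassification rate can be given.

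The consequence is confined to one descriptive secondary endpoint in 10 to 18 patients, with no hypothesis test. The primary endpoint, Overall Response and survival are not affected.

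**What to change.** 1. Check the formula on the issued SAP page and in the program, and state BSA (m²) = √(height (cm) × weight (kg) / 3600).
2. For *Other*, derive administrations per day from the recorded dosing detail. Protocol 6.4.5 already requires it: "Information about medication name, indication, dose, unit, frequency, route date and time is to be recorded for each medication". Query *Unknown* before database lock. Keep the value 1 only for records that stay unresolved, including *As needed* records without usable detail, and report how many patients they affect.
3. State which height and weight enter post-baseline doses. A single baseline value, which is equivalent to comparing daily mg of dexamethasone-equivalent, keeps weight change out of the 50% endpoint. If current weight is preferred, say so.
4. Give the unit of the equivalent dose in SAP 6.5. It would also help to say that all same-day glucocorticoid records are summed, including records of the same drug.

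The cost is one formula check, a few sentences in the SAP, a revised lookup rule and some data queries before lock. No new assessments are needed.

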#### Investigator Assessed Response

The treatment policy strategy will be applied. The investigator assessed response will be estimated as described below regardless of any potential intercurrent events.

In addition to Overall Response assessed by programmed algorithm, achievement of response assessed by investigator (Complete Response, Partial Response, or No Response) will also be collected in the CRF during the treatment period. The number and percentage of subjects achieved each category of investigator assessed response by visit will be presented.

#### Survival to Start of HSCT Conditioning

The treatment policy strategy will be applied. Survival to start of HSCT will be estimated as described below regardless of any potential intercurrent events.

Survival to start of HSCT conditioning is defined as time from first dose of emapalumab to date of death from any cause, with censoring time at date of the start of conditioning for HSCT (or last contact, if patient did not undergo HSCT) for patients with no event ([refer to Section 6.2.2](#)).

Survival to start of HSCT conditioning will be estimated applying Kaplan-Meier methodology. Median survival time, 75th and 25th percentiles will be calculated where available with associated

two-sided 95% confidence intervals. Survival rates and associated two-sided 95% confidence intervals will be calculated at day 7 (1 week), day 14 (2 week), day 21 (3 week), day 30, day 60, day 100, day 180 (6 month) and day 360 (12 month).

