4.3.1 Potential benefits

Based on evidence available from comprehensive analysis of the NI-0501-04 and NI-0501-05 studies, emapalumab administration has shown the overall potential to improve or resolve relevant clinical and laboratory abnormalities of pHLH.

Also, in the cohort of the treatment experienced patients which corresponds to the patient population of the current study, emapalumab demonstrated a statistically significant and clinically relevant reduction in pHLH disease activity, the Overall Response Rate (ORR) was assessed through objective clinical and laboratory parameters as being 58.8% (20/34 patients). Response occurred early during treatment (the median time to response was 7.0 days) and was generally sustained. The median cumulative time at which the patients remained “in response” was 31.5 days and in 75% of patients the first response was maintained for at least 22 days. The reduction in HLH disease activity was sustained and was associated with an overall survival benefit that persisted following HSCT. 27 of 34 patients (79.4%) survived to HSCT and the post-HSCT survival probability estimates were 91% (95% CI: 68.3%, 97.6%) at 3 months and 89% (95% CI: 64%, 97%) at 1 year post-HSCT. The observed treatment effect was consistent across all efficacy endpoints.

Emapalumab was well tolerated in doses up to 10 mg/kg and no off-target toxicity has been identified.

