6.5.4.5 HSCT

Information about conditioning for HSCT and of the HSCT will be recorded in the eCRF. This information will be used to calculate the number and proportion of patients able to commence conditioning for HSCT

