	
Secondary Endpoint 6: Survival to start of HSCT conditioning, i.e., time from the date of first dose of Emapalumab to date of death, with censoring at conditioning for HSCT or at last date of contact for patients who did not undergo conditioning for HSCT
	
Estimand 2.6
 
Target population: All patients received at least one infusion of IMP
 
Treatment: Refer to Section 6.4 in study protocol
 
Endpoints: Refer to the left column
 
Strategies for addressing intercurrent events:
 
The treatment policy strategy will be applied for the estimand
 
Population-level summary: Survival to start of HSCT conditioning will be estimated using Kaplan-Meier method

	
Secondary Endpoint 7: Survival after HSCT, i.e., time from HSCT to death, with censoring time at last date of contact for patients with no event.
	
Estimand 2.7
 
Target population: All patients received at least one infusion of IMP and underwent HSCT
 
Treatment: Refer to Section 6.4 in study protocol
 
Endpoints: Refer to the left column
 
Strategies for addressing intercurrent events:
 
The treatment policy strategy will be applied for the estimand
 
Population-level summary: Survival after HSCT will be estimated using Kaplan-Meier method

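### Survival to HSCT conditioning is a Kaplan-Meier curve censored at conditioning, so it does not estimate the chance of reaching conditioning alive and does not fit the declared treatment policy strategy

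*SAP*

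**What the plan says.** SAP 6.8.2, Survival to Start of HSCT Conditioning, sets the event and time origin: "Survival to start of HSCT conditioning is defined as time from first dose of emapalumab to date of death from any cause". It sets the censoring rule: "with censoring time at date of the start of conditioning for HSCT (or last contact, if patient did not undergo HSCT". SAP 6.2.2 and protocol 8.3.4.3 also censor at the start of conditioning. The estimator is given in SAP 6.8.2 ("Survival to start of HSCT conditioning will be estimated applying Kaplan-Meier methodology") and in Estimand 2.6 ("Survival to start of HSCT conditioning will be estimated using Kaplan-Meier method").

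On output, the SAP says: "Survival rates and associated two-sided 95% confidence intervals will be calculated at day 7 (1 week", continuing through days 14 and 21 to "day 30, day 60, day 100, day 180 (6 month) and day 360 (12 month". Both SAP sections declare a treatment policy strategy, and 6.8.2 adds that intercurrent events are disregarded.

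Two other places bear on the point. Protocol 4.3.1 reports from earlier work that "27 of 34 patients (79.4%) survived to HSCT", which is a simple proportion. Protocol 6.5.4.5 says the recorded transplant data will be used to calculate the "number and proportion of patients able to commence conditioning for HSCT".

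**The concern.** Inclusion criterion 6 requires an expectation of proceeding to HSCT, and protocol 6.2 expects treatment to last until conditioning starts. Conditioning is therefore the planned exit. Once it starts, death before conditioning can no longer happen, so it is a competing event. Censoring there makes Kaplan-Meier treat conditioned patients as if they went on facing the pre-conditioning death risk of those still waiting. The result is survival in a setting without conditioning, and it is valid even for that only if the timing of conditioning is unrelated to prognosis.

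The declared strategy does not match. Treatment policy means that follow-up counts whether or not the intercurrent event happens. Here follow-up stops at the main intercurrent event, which is in effect a hypothetical strategy.

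For a drug used as a bridge to transplant, the natural question is how many patients reach conditioning alive. The endpoint's label invites a reader to take the curve as the answer. Its late values may look much worse, or better, than that proportion, and they may rest on almost nobody.

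**Working it through.** **Inputs from the documents.** N is 10 to 18 (SAP section 2). The only figure for reaching transplant alive is the one in protocol 4.3.1: 27/34 = 79.4%, which reproduces. The complement is 7/34 = 20.6%. The documents give no event count, assumed rate or timing for this endpoint.

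**Assumptions.** Hazards are constant. Every patient is eventually conditioned or dies, and the share dying first is d = 0.206. The median time to whichever comes first is 75 days, varied from 45 to 120. Protocol 4.3.1 does not say that the other 7 of 34 died; reading them as deaths is an assumption.

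**Formulas.** With λ = ln 2 / median and S(t) = exp(−λt):
- Kaplan-Meier, conditioning censored: exp(−dλt)
- Not dead before conditioning: 1 − d(1 − S)
- Conditioning started alive: (1 − d)(1 − S)
- Expected number at risk: N × S

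**Median 75 days** (λ = 0.00924 per day).
- Day 180: S = 0.189. Kaplan-Meier is exp(−0.343) = 71%. Not dead before conditioning is 1 − 0.206 × 0.811 = 83%. Conditioned is 0.794 × 0.811 = 64%.
- Day 360: S = 0.036. Kaplan-Meier is exp(−0.685) = 50%. Not dead before conditioning is 1 − 0.206 × 0.964 = 80%. Conditioned is 0.794 × 0.964 = 77%.

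**Range of medians.**

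| Median (days) | Landmark | Kaplan-Meier | Not dead before conditioning | Conditioned |
|---|---|---|---|---|
| 45 | day 180 | 56.5% | 80.7% | 74.4% |
| 45 | day 360 | 31.9% | 79.5% | 79.1% |
| 120 | day 180 | 80.7% | 86.7% | 51.3% |
| 120 | day 360 | 65.2% | 82.0% | 69.5% |

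At day 180 Kaplan-Meier is above the conditioned proportion with a median of 75 or 120 days and below it with 45.

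**Dependence on the order of events.** Take 18 patients, 14 conditioned and 4 dead, so that the proportion reaching conditioning alive is 14/18 = 77.8%. The final Kaplan-Meier value depends only on the order:
- All deaths before the first conditioning: 14/18 = 77.8%, equal to the proportion.
- Deaths when 18, 15, 10 and 5 are at risk: 17/18 × 14/15 × 9/10 × 4/5 = 63.5%.
- The last patient at risk dies: 0%.

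**Patients who stay alive without conditioning.** Simulated trials used N = 18, a mean exit time of 75 days, 27/34 of exits being conditioning, and unconditioned survivors followed to day 540. Mean day-360 values were:

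| Alive, never conditioned | Kaplan-Meier | Conditioned | Trials with Kaplan-Meier lower |
|---|---|---|---|
| 0% | 49.1% | 78.7% | 96% |
| 5% | 57.3% | 74.9% | 80% |
| 10% | 64.4% | 71.0% | 57% |
| 20% | 71.8% | 62.9% | 26% |
| 30% | 78.5% | 55.0% | 6% |

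Kaplan-Meier never exceeded the proportion not dead before conditioning in any simulated trial.

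**Late risk sets.** With a 75-day median and everyone resolved, the expected number at risk for N = 10 to 18 is 1.9 to 3.4 at day 180 and 0.4 to 0.6 at day 360. The chance that nobody is at risk at day 360 is (1 − 0.036)^N: 69% for N = 10 and 52% for N = 18. With a 120-day median, 1.3 to 2.3 would be at risk at day 360.

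**The case against.** The endpoint is defined openly, and protocol and SAP agree that it is time to death censored at conditioning. Neither calls the curve the chance of reaching conditioning, and neither plans a comparison with 79.4%. SAP 6.8.2 also includes overall survival from first dose, not censored at conditioning, at the same landmarks. The analysis is secondary and descriptive, with no hypothesis test and few expected deaths. All of this stands and limits the consequence. It does not make the curve an estimate of reaching conditioning alive, and overall survival does not fill the gap because it mixes deaths before and after transplant.

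Three stronger readings are tempting, and the documents do not support them.

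- *The curve understates the chance of reaching conditioning alive.* The direction is not fixed. At day 180 in the worked model it overstates it (71% against 64%). The earlier study's treatment-experienced group (70% of 27 transplanted, about 19; 74% alive, about 20) allows from 1/27 (20 − 19) to 8/27 (27 − 19) alive without transplant. That is 3.7% to 29.6%, a range over which the direction at day 360 switches.
- *The late values concern only patients never conditioned.* A Kaplan-Meier value is a product over all earlier risk sets, which include patients conditioned later. Protocol 6.5.1.4 also allows for donor searches longer than 6 months, so patients at risk at day 180 may still be conditioned.
- *The SAP omits the proportion starting conditioning.* No visible SAP section gives it for all treated patients; SAP 6.3 reports HSCT among those who completed treatment. But protocol 5.2.2 and 8.3.5 and SAP 6.9 show headings without text and may be blacked out, so the proportion cannot be called absent.

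**Conclusion.** The point holds in limited form. The planned curve is net survival as if conditioning did not occur, under independent censoring, and this conflicts with the declared treatment policy strategy. Both statements follow from the SAP text and need no assumption.

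The curve's values are at most equal to the probability of not having died before conditioning, with equality if all deaths precede the first conditioning. Under the 75-day assumptions the shortfall is 12 percentage points at day 180 (83 − 71) and 30 at day 360 (80 − 50). For medians of 45 to 120 days the day-360 shortfall runs from 48 to 17 points. These sizes rest on constant hazards, on assumed timing and on every patient being conditioned or dead; early deaths would shrink or remove the gap. Under the 75-day assumptions the day-360 risk set would usually be empty or hold one patient.

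This should be changed because a clearer estimate needs no new data, but no formal conclusion of the trial depends on it.

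**What to change.** 1. Add to SAP 6.8.2 the Aalen-Johansen cumulative incidence, from first dose in the All treated set, of death before conditioning and of conditioning started alive, at the landmarks already listed.
2. Add the number and percentage of all treated patients starting conditioning, as protocol 6.5.4.5 foresees, with a Clopper-Pearson interval, unless a blanked section already plans this. The SAP already uses that interval for overall response. For illustration, 14/18 = 77.8% would carry a 95% interval of 52.4% to 93.6%.
3. Keep the protocol-defined Kaplan-Meier curve, labelled as censored at conditioning and shown with numbers at risk at each landmark.
4. In Estimand 2.6 and SAP 6.8.2, replace the treatment policy wording for this endpoint. Describe the Kaplan-Meier curve as hypothetical with respect to conditioning, and the cumulative incidences as treating conditioning and prior death as competing first events.

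Conditioning and transplant information is already recorded in the eCRF. The cost is SAP wording and about one extra table in a descriptive secondary analysis.
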